5.1.3 Exploratory Endpoints

- Changes in tumor size assessed by IIR using volumetric CT/MRI

- Immune pharmacodynamics effects of E7766 in the tumors and in the peripheral blood
- PK/pharmacodynamics relationships (safety and efficacy endpoints)
- Baseline immune phenotypes and its relationship with the response to E7766
- STING genotypes and its relationship with the response to E7766
- Changes in pre-injection size of injected lesion per investigator assessment

5.2 Study Subjects

5.2.1 Definitions of Analysis Sets

DLT Analysis Set is the group of subjects in the Dose Escalation part who have completed Cycle 1, without incurring certain major protocol deviations (for instance those related to dosing or others identified before database lock), with at least 2 E7766 injections during Cycle 1, and are evaluable for DLT, or subjects who have experienced DLT during Cycle 1. This will be the analysis set to evaluate tolerability.

Full Analysis Set is the group of subjects who received at least 1 dose of study drug. This will be the primary analysis set for efficacy evaluations, as well as for demographic and baseline characteristics.

Safety Analysis Set is the same group as Full Analysis Set. This will be the analysis set for all safety evaluations except DLT results.

Efficacy Analysis Set is the group of subjects who received at least 1 dose of study drug and had a baseline tumor assessment. This will be used for supportive analysis of ORR.

Pharmacodynamic Analysis Set and Pharmacokinetic/Pharmacodynamic Analysis Set are defined in separate PK or PK/PD analysis plan(s).

5.2.2 Subject Disposition

The number (percentage) of enrolled (i.e., signed informed consent) and treated subjects will be summarized as well as subjects who completed the study or discontinued from the study, with reasons for discontinuation.

The number (percentage) of subjects who completed the study treatment/discontinued from the study treatment and reasons for discontinuation will also be summarized.

Subject data listings for the disposition of screening, treatment, and study will be provided.

5.2.3 Protocol Deviations

All major protocol deviations will be determined and documented based on the review of individual subject data prior to database lock.

Major protocol deviations will be listed and summarized on Full Analysis Set.

5.2.4 Demographic and Other Baseline Characteristics

Demographic and other baseline characteristics for the Full Analysis Set will be summarized using descriptive statistics.

Continuous demographic and baseline variables including age, weight, height and time since first diagnosis (months) will be summarized and presented as N, mean, standard deviation, median, Q1, Q3, minimum and maximum values.

For categorical variables such as sex, age group (e.g., <65, >=65), race, ethnicity, geographic region, Eastern Cooperative Oncology Group (ECOG) performance status, New York Heart Association (NYHA) cardiac disease classification, type of tumor diagnosis, location of primary tumor, histology/cytology of the primary tumor, and tumor staging (tumor-node-metastasis [TNM] classification), the number and percentage of subjects will be presented.

Previous therapies (anticancer medication, procedure, and radiotherapy) will also be listed and summarized.

Medical History

The history of any medical condition, as recorded on the case report form (CRF), will be listed.

5.2.5 Prior and Concomitant Therapy

All investigator terms for medications recorded in the CRF will be coded to an 11-digit code using the World Health Organization Drug Dictionary (WHO DD) Version of March 2019 or later.

The number (percentage) of subjects who took prior and concomitant medications will be summarized on the Full Analysis Set by Anatomical Therapeutic Chemical (ATC) class (ie, Anatomical class, Pharmacological class) and WHO DD preferred term. Prior medications will be defined as medications that started before the first dose of study drug. Concomitant medications will be defined as medications that (1) started before the first dose of study drug and were continuing at the time of the first dose of study drug, or (2) started on or after the date of the first dose of study drug up to 90 days after the subject's last dose. Note that a medication can be classified as both prior and concomitant, if the medication started before the first dose of study drug and continued after the first dose.

All medications will be presented in subject data listings.

Anticancer therapies (medication, procedure) received during survival follow-up will also be listed.

5.2.6 Treatment Compliance

Treatment compliance related major protocol deviations will be presented as provided in [Section 5.2.3](#). Information on subject exposure to study drug is described in [Section 5.6.1](#).

5.3 Data Analysis General Considerations

5.3.1 Pooling of Centers

Subjects from all centers will be pooled for all analyses.

5.3.2 Adjustments for Covariates

No adjustment for covariates will be performed.

5.3.3 Multiple Comparisons/Multiplicity

No statistical comparisons will be performed for this study.

5.3.4 Examination of Subgroups

Subgroup analyses may be conducted, if deemed appropriate.

5.3.5 Handling of Missing Data, Dropouts, and Outliers

Treatment Related TEAEs include TEAEs that were considered by the Investigator to be related to study drug or TEAEs with a missing causality.

Medications will be considered concomitant if:

- a) Day and month are missing and the year is equal to or after the year of the first dose date;
- b) Day is missing, and the year is after the year of the first dose;
- c) Day is missing and the year is equal to the year of the first dose date and the month is equal to or after the month of the first dose date; or
- d) Year is missing; or
- e) Complete date is missing.

For efficacy endpoints, missing assessments will not be imputed. For incomplete dates involving efficacy and safety data such as adverse events, concomitant medications, laboratory assessments, vital signs, and echocardiogram/multigated acquisition (MUGA) data, a conservative imputation will be used for calculation if needed. The imputation rules will be specified in study analysis dataset specification with more details.

5.3.6 Other Considerations

Improved Modified Toxicity Probability Interval Design (mTPI-2) in Dose Escalation Part

The mTPI-2 design, which uses a Bayesian statistical framework and a beta-binomial hierarchical model, will be employed to determine the MTD and/or RP2D of E7766.

Decision rules for dose assignment will be based on the mTPI-2 design with the target DLT rate of 25% and its equivalence interval (EI) of 20% to 30%, and a set of equal-width intervals as EI below/above EI (ie, below EI: 0% to 10%, 10% to 20%; above EI: 30% to 40%, ... , 90% to 100%). The posterior probabilities of each interval will be calculated with non-informative beta prior distribution Beta (1, 1). The location of the interval with the largest posterior probability—below EI, EI, or above EI—guides the decision for the next dose level to be assigned, ie, Dose Escalation (E), Staying at the current dose (S), or dose De-escalation (D), respectively. This dose assignment rule minimizes the posterior expected penalty in the Bayes' rule under a decision-theoretic framework with the equal prior expected penalties for E, S, and D. The entire dose assignment decision rule can be pre-tabulated as presented in [Table 1](#).

The subject enrollment will be closed when the lowest dose has a >95% posterior probability of being above the target DLT rate of 25% (ie, an unacceptable DLT rate beyond the target DLT rate) or when the RP2D has been determined.

The MTD is defined as the dose with the smallest difference between the target DLT rate of 25% and an estimate of DLT rate at each dose among all the tested doses with a $\leq 95\%$ posterior probability of being above the target DLT rate of 25%. The isotonically transformed posterior mean under the beta posterior distribution with non-informative beta prior distribution Beta (0.005, 0.005) will be used to determine the estimate of DLT rates at each dose. The pooled adjacent violators algorithm (PAVA; [Bartholomew et al., 1983](#)) will be used to maintain monotonically the increase of DLT rate with increasing dose level. Late immune-related toxicities occurring after Cycle 1 (DLT period) and up to 90 days after last dose of E7766, will also be used to inform corrections to the MTD and aid selection of the RP2D.

5.4 Efficacy Analyses

All efficacy analyses will be primarily performed on the Full Analysis Set. As supportive analysis, summary of ORR will also be performed on the Efficacy Analysis Set.

5.4.1 Primary Efficacy Analyses

5.4.1.1 Dose Escalation Part

There will be no primary efficacy analysis since the primary objective of the Dose Escalation part is to assess the safety/tolerability and to determine the MTD and/or RP2D. Thus, the efficacy analyses are described in the subsequent sections according to the study endpoints.

5.4.1.2 Dose Expansion Part

Objective Response Rate

ORR will be calculated with exact 95% confidence interval (CI) using Clopper and Pearson method. Summary of best overall response will be provided.

For subjects with solid tumors, swimmer plots based on modified RECIST 1.1 may also be presented as appropriate.

Duration of Response

DOR will be summarized using Kaplan-Meier estimates as appropriate. Median, Q1, Q3, and their 95% CIs estimated using generalized Brookmeyer and Crowley method will be presented. Kaplan-Meier estimates of DOR will be plotted over time. The DOR will be based on subjects achieving a best overall response of confirmed PR or CR.

Disease Control Rate

DCR will be calculated with exact 95% CI using Clopper and Pearson method.

5.4.2 Secondary Efficacy Analyses

5.4.2.1 Objective Response Rate for Dose Escalation Part

ORR for Dose Escalation part will be evaluated in the same manner as described in Section 5.4.1.2 for Dose Expansion part.

5.4.2.2 Duration of Response for Dose Escalation Part

DOR for Dose Escalation part will be evaluated in the same manner as described in Section 5.4.1.2 for Dose Expansion part.

5.4.2.3 Disease Control Rate for Dose Escalation Part

DCR for Dose Escalation part will be evaluated in the same manner as described in Section 5.4.1.2 for Dose Expansion part.

5.4.2.4 Progression-free Survival

In PFS analysis Subjects without disease progression or death will be censored at the time of the last tumor assessment. Subjects who started new anticancer therapies without documented progression of disease will be censored at the last adequate tumor assessment on or prior to the start of new anticancer therapies. Determination of the date of PFS event or censoring is summarized in [Table 3](#) below.

Table 3 PFS Event and Censoring Rules

No.	Situation	Date of Progression or Censoring	Outcome
1	No baseline or postbaseline adequate tumor assessments	Date of first dose	Censored
2	Progression documented between scheduled visits, on or prior to new anticancer therapy	Date of first qualified*** PD assessment	PFS Event
3	No progression at the time of data cutoff	Date of last adequate assessment on or prior to data cutoff	Censored
4	New anticancer therapy started	Date of last adequate assessment on or prior to the start of new anticancer therapy	Censored
5	Death before first PD assessment, on or prior to start of new anticancer therapy	Date of death	PFS Event
6	Death between adequate assessment*	Date of death	PFS Event
7	Death or progression after more than one missed visit/tumor assessment**	Date of last adequate assessment before missed tumor assessments	Censored

CR = complete response, ic = iRECIST-confirmed, iu = iRECIST-unconfirmed, PD = progressive disease, PR = partial response, SD = stable disease.

Note:

* Adequate tumor assessment is radiologic assessment of CR, PR, SD, non-CR/non-PD or PD as determined by investigators at regular interval as defined in the protocol. Any tumor assessments after new anticancer therapy will not be considered in the definition of PFS.

** More than one missed visit/adequate tumor assessment is defined as:

- having the duration between two consecutive tumor assessments or the duration between the last adequate tumor assessment and death/PD being longer than (>) 97 days (for solid tumors because the scans are scheduled every 6 weeks \pm 7 days for this study).

*** Qualified PD is defined as:

- For modified RECIST: the documented PD per modified RECIST CRF page;
- For iRECIST: in the order of 1) the documented iCPD per iRECIST CRF page, or 2) the iUPD that has not be reset by subsequent iCR/iPR/iSD

NOTE: iCPD has to be within 8 weeks of iUPD, but not earlier than 4 weeks (i.e. \geq 28 days) of iUPD.

1. If the subject had PD or death, the following sequence will be applied:

- If a subject did not have baseline or postbaseline adequate tumor assessments (No. 1), the subject will be censored at the date of the first dose. However, if the subject died within 35 days after the first dose date and did not receive any new anticancer therapy, it will be counted as a PFS event at the date of death.
- If subject has baseline tumor assessment but does not have any postbaseline adequate tumor assessments, the subject will be censored at the date of the first dose. However, if the subject died

within 97 days after the first dose date and did not receive any new anticancer therapy, it will be counted as a PFS event at the date of death.
 
 • If a subject has a baseline and at least one post-baseline adequate tumor assessment and had new anticancer therapy before PD or death (No. 4), the subject will be censored at the date of the last adequate tumor assessment on or prior to the date of new anticancer therapy • If a subject missed two or more tumor assessments (No. 7), the subject will be censored at the date of the last adequate tumor assessment before the occurrence of more than one missing assessment. Note that if a subject is censored by both of this criterion and start of new anticancer therapy criterion, the earliest censoring date will be used. • Otherwise, if a subject had PFS event (No. 2, No. 5 or No. 6), the earliest event date will be used. 
2. If a subject did not have PD or death, the censoring date will be the earliest censoring date if the subject met multiple censoring criteria (No. 1, No. 3, No. 4, No. 7).

PFS will be presented in subject data listings.

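### Read literally, the SAP's PFS rule censors before any scan gap of more than 97 days, even when a later scan shows no progression and the eventual PD is found on schedule

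*SAP*

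**What the plan says.** All of this is in SAP 5.4.2.4, Table 3 and its notes.

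- **Row 7** covers "Death or progression after more than one missed visit/tumor assessment" and censors at "Date of last adequate assessment before missed tumor assessments".
- **The double-asterisk note** sets the trigger with the words "having the duration between two consecutive tumor assessments or the duration between the last adequate tumor assessment and death/PD being longer than", the limit being 97 days. It states this for solid tumors and ties it to the six-weekly scan schedule and its window of 7 days on either side.
- **Item 1** (subjects with PD or death) lists the rules in order. For two or more missed assessments, "the subject will be censored at the date of the last adequate tumor assessment before the occurrence of more than one missing assessment". The event rule comes after this bullet and takes only the subjects left over. No exception is made for a later scan without progression.
- **Item 2** (subjects with neither PD nor death) says "the censoring date will be the earliest censoring date if the subject met multiple censoring criteria (No. 1, No. 3, No. 4, No. 7".
- **Row 3** gives the censoring date for a subject who has not progressed at the data cutoff as "Date of last adequate assessment on or prior to data cutoff". The opening sentence of the section and protocol 9.7.1.6.2 likewise censor subjects without an event at their last tumor assessment. The protocol has no gap rule.

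**The concern.** Gap censoring exists because the timing of an event found after a long unobserved stretch is uncertain. The second half of the note, from last adequate assessment to death or PD, already covers that case. What the first half adds is gaps that a later scan without progression has closed, where most of that uncertainty is gone. Applying the rule there discards the later scan and everything after it, including a PD found between two on-time scans.

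For subjects without an event, the SAP supports two answers: row 3 and the opening sentence give the last assessment, while item 2 gives the assessment before the gap. Two programmers could derive different PFS dates for the same subject.

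PFS is not among the analyses dropped in SAP section 7, and it still goes into the subject listings, so the date matters for each subject affected. Section 7 does drop the tumor assessment listings, which makes such a date harder to trace from the report.

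**Working it through.** **Inputs from the documents.** Limit of more than 97 days; scans every 42 days with a window of 7 days either way (SAP 5.4.2.4); about 35 escalation subjects anticipated (SAP section 4).

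**1. The limit itself.** The SAP does not show how 97 was derived, but 2 × 42 + 2 × 7 − 1 = 97 reproduces it. The longest gap with one missed scan is 2 × 42 + 14 = 98 days, and the shortest with two missed is 3 × 42 − 14 = 112 days. The limit separates the two cases except at the single extreme value of 98. The length is not the problem; which gap it is applied to is.

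**2. The two rules.** Let the assessments fall on days s₀ = 0, s₁, …, sₙ.

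- *As written:* at the first j with sⱼ − sⱼ₋₁ > 97, censor at sⱼ₋₁. If there is none, use sₙ (event if PD, otherwise censored).
- *Gap before the event only:* if sₙ is PD and sₙ − sₙ₋₁ > 97, censor at sₙ₋₁. Otherwise use sₙ.

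**3. Worked cases.**

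| Scans (day) | Last scan | As written | Gap before event only |
|---|---|---|---|
| 42, 84, 210, 252 | PD | censored, day 84 | event, day 252 |
| 42, 84, 210, 252 | no PD | censored, day 84 | censored, day 252 |
| 42, 84, 252 | PD | censored, day 84 | censored, day 84 |

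In the first two cases the gap is 210 − 84 = 126 days, and the SD scan at day 210 closes it. The rule as written removes 252 − 84 = 168 days of follow-up and, in the first case, a documented PD found 42 days after the previous scan. In the third case the gap of 252 − 84 = 168 days directly precedes the PD and both rules censor, so the narrower rule keeps the legitimate purpose.

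**4. Likely size.** The documents give neither a miss rate nor an expected PFS, so these are assumptions: exponential PFS with median 90 or 180 days, up to 8 six-weekly scans, each missed independently, and 200,000 simulated subjects per scenario, scaled to 35.

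| Median PFS | Scans missed | Events, as written | Events, narrower rule | Subjects changed | Follow-up kept |
|---|---|---|---|---|---|
| 90 d | 5% | 32.12 | 32.18 | 0.10 | 99.55% |
| 90 d | 10% | 31.36 | 31.58 | 0.36 | 98.37% |
| 90 d | 20% | 29.01 | 29.74 | 1.30 | 94.08% |
| 180 d | 5% | 25.11 | 25.20 | 0.21 | 99.33% |
| 180 d | 10% | 24.45 | 24.72 | 0.78 | 97.47% |
| 180 d | 20% | 22.08 | 23.01 | 2.85 | 90.66% |

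Across the range, 0.1 to 2.9 of 35 subjects change, 0.1 to 0.9 events are lost, and total PFS follow-up falls by about 0.5% to 9%.

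**5. Shorter follow-up.** Cutoff six months after the last subject starts allows a late enrollee about 4 scheduled scans. The chance that two or more consecutive missed scans are followed by a completed one is then 2p²(1 − p): 0.5%, 1.8% and 6.4% at p = 5%, 10% and 20%. With 8 scheduled scans, exact enumeration gives 1.4%, 5.4% and 18.6%. Both sets include cases where the closing scan is itself PD, which the two rules treat alike, so they are upper bounds on the subjects affected.

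**The case against.** **A later stable scan does not settle what happened in the gap.** The protocol anticipates transient tumor flare followed by response (9.5.1.3.1 and Appendix 2). For modified RECIST PFS, any documented PD counts; only iRECIST resets after a later iSD, iPR or iCR. A flare on a missed scan would have been a modified RECIST event, and the later SD scan cannot exclude it. Missed scans may also hide the nadir from which PD is judged. This stands: a reader might infer that a closed gap leaves nothing unknown, and the documents do not support that. What the later scan does is remove most of the uncertainty, and the SAP does not offer flare as the reason for its rule.

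**The text may be milder than it looks.** Row 7's wording could mean immediately after the missed visits. Item 2 could be read as a tie-break in which No. 7 never bites, since a subject with neither PD nor death does not fit row 7's label. Row 7 alone is indeed ambiguous. But the consecutive-assessment wording in the note has no work to do under the milder reading, item 1 has no such limit, and item 2 names No. 7 expressly for subjects without an event. At best the SAP can be read two ways.

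**Few subjects are affected.** This also stands. The expansion part was cancelled (SAP 3.2.2), escalation ended early without an MTD (section 7), and no statistical comparisons are made (5.3.3). A reader might infer that only subjects with the longest disease control are hit; in fact two missed scans and one later scan suffice, and longer follow-up merely raises the chance. Nor do the documents tie any dose decision to the PFS tail.

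**Conclusion.** The point holds in a limited form. Followed literally, SAP 5.4.2.4 moves censoring back to before a gap that a later scan without progression has closed, and can thereby turn a PD found on schedule into a censored observation. For subjects without an event it conflicts with row 7's label, row 3, its own opening sentence and protocol 9.7.1.6.2; section 7 does not list this as a change. These conflicts rest on the text alone.

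The size rests on the assumed miss rates (5% to 20%), independent misses, exponential PFS and up to 8 scans: roughly 0 to 3 of about 35 subjects, mainly in the tail of the curve and the listings. Shorter follow-up would make it smaller. It is worth correcting because the rule gives a wrong date for the subjects it catches and cannot be programmed unambiguously, not because it threatens the trial's conclusions.

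**What to change.** Three linked edits to SAP 5.4.2.4:

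1. In the double-asterisk note, delete the part about two consecutive assessments. Define No. 7 as PD or death more than 97 days after the last adequate assessment *before that PD or death*. The word *before* is needed because the single-asterisk note counts a PD scan as adequate, so the interval could otherwise be read as zero.
2. Reword the item 1 bullet, which is the operative sentence: *If the PD or death occurred more than 97 days after the last adequate tumor assessment preceding it (No. 7), the subject will be censored at that assessment.*
3. Delete No. 7 from item 2, so that subjects without an event are censored at the last adequate assessment as in row 3, still subject to the new-anticancer-therapy rule (No. 4).

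The cost is SAP wording and one programming rule. No additional data are needed.

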#### 9.4.1.1 Dosing Schedules

E7766

A fully equipped and functional crash cart must be available in the unit where a subject is to be administered E7766.

E7766 will be administered in 3-week cycles, with treatment as follows:

- Induction (Cycle 1): Days 1, 8, 15
- Maintenance (Cycle 2 and after): on Day 1 of each cycle, Q3W.

In the Maintenance treatment portion, ie, Cycle 2 forward, if a scheduled dosing is missed or delayed, this dosing will be administered as soon as allowed under dose interruption/retreatment guidelines. Treatment cycles will be synchronized to the new dosing day, ie, the day of administration of the made-up dosing will be considered Day 1 of the next cycle. This synchronization will include all cycle Day 1 assessments and procedures, but will exclude response assessments as outlined in Section 9.5.1.3.

Eisai Confidential Page 65 of 138

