# **Tumor assessments during study:**

- CT scans for head, neck, abdomen and pelvis will be carried out every 6 weeks (± 7 days) counting from Cycle 1 Day 1 during treatment cycles in the Treatment Phase, the Extension Phase, and, if the subject has discontinued treatment without confirmed disease progression, the Follow-Up Phase.
  - MRI scans may be used instead of CT scans for head, neck, abdomen and pelvis; however, chest lesions must be assessed using CT. Chest disease may not be followed using chest x-ray. The same method of assessment must be used at all time points as used at Screening
- **Bone scans:** For subjects with triple-negative breast cancer and non-small-cell lung carcinoma, or other tumor types where bone metastases are common, bone scans will be performed every 24 weeks, or sooner if clinically indicated, and at confirmation of response. Lesions identified on bone scans must be verified with correlative cross-sectional imaging. Cross sectional imaging will be used to follow response in target and nontarget lesions.
- Brain MRI

Eisai Confidential Page 76 of 138

- For subjects with protocol-eligible treated brain metastases (See Exclusion Criterion #7) detected at the Screening MRI brain, a brain scan must be performed at all tumor assessment time points.
- For all subjects, a follow-up brain scan must be performed to confirm a CR within 1 week following response confirmation, or if clinically indicated.

For definitions of target and nontarget lesions at Baseline, assessment of target, nontarget, and new lesions after Baseline, and overall tumor assessment using iRECIST, refer to Appendix 1 and Appendix 2.

Responses should be confirmed no less than 4 weeks following the initial response (generally at the next 6 weekly scheduled tumor assessment visit).

Tumor assessments should initially proceed according to modified RECIST 1.1.

Per iRECIST, disease progression should be confirmed by the site 4 to 8 weeks after site-assessed first radiologic evidence of progressive disease in clinically stable subjects. Subjects who have unconfirmed progressive disease per iRECIST (iUPD) may continue on treatment at the discretion of the investigator until progression is confirmed by the site, provided they have met the following conditions.

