- s. Solid tumor assessments will be performed based on modified RECIST 1.1 followed by modified RECIST 1.1 for immune-based therapeutics (iRECIST), if appropriate. Tumor assessments will be carried out during the Pretreatment Phase and then every 6 weeks (±7 days, counting from Cycle 1 Day 1) during treatment cycles in both the Treatment Phase and the Extension Phase. CT scans (with oral and intravenous contrast) of chest, abdomen, and pelvis and of other known sites of disease will be obtained at Screening (within 28 days prior to Cycle 1 Day 1), and subsequently using the tumor assessment schedule above, and as indicated clinically. Skin lesions may be considered as target lesions if color photographs are available and measurement documented; else can be considered only as nontarget lesions (ie, without photographic or measurement documentation).

Subjects with HNSCC must also have head and neck scans performed. Historical standard of care scans that are performed with scanning parameters

Eisai Confidential Page 92 of 138

	Phase	PRETREA	TMENT a			TRE	ATMEN	T b		E	XTENSI	ON	Off- Treatment b	FOLLOW- UP PHASE
	Period	Screening	Baseline	Cycle 1 (Induction Cycle)						Cyc	le 2	Cycle 3 and beyond	Within 30 days	
	Visit	1	2	3	3 3 4 5 5 5					6	7	8, 9, etc	98	100
	Day	-28 to -1	-3 to -1	1	1 2 8 14 15 16					1	15	1		
CRF	Procedures/Assessments													

consistent with the requirements for this protocol within 28 days prior to dosing are acceptable.

MRI scans may be used instead of CT scans for head, neck, abdomen and pelvis; however, chest lesions must be assessed using CT. Chest disease may not be followed using chest x-ray. CT scans should be performed with oral and iodinated IV contrast and MRI scans with IV gadolinium chelate unless there is a medical contraindication to contrast. If iodinated IV contrast is contraindicated, a chest CT should be performed without IV contrast. The method of assessment must be consistent at all time points.

In the Follow-Up Phase, subjects going off study without disease progression will also undergo tumor assessments every 6 weeks ( $\pm 7$  days) until disease progression is documented or another anticancer therapy is initiated.

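### The 97-day cut-off for more than one missed scan is one day short of the schedule that justifies it: a single missed scan can span 98 days

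*SAP*

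**What the plan says.** SAP Section 5.4.2.4, Table 3, row 7 censors a death or progression that follows more than one missed assessment, at the last adequate assessment before the gap. The double-asterisk footnote turns this into days: the time between two consecutive assessments, or from the last adequate one to death or progression, "being longer than (>) 97 days". Its stated reason is "for solid tumors because the scans are scheduled every 6 weeks", with a window of 7 days either side. The sequence notes under the table describe the same rule in counts: "If a subject missed two or more tumor assessments (No. 7".

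The protocol fixes the scan calendar. Table 7, footnote s, schedules solid-tumor scans "every 6 weeks (±7 days, counting from Cycle 1 Day 1", and Section 9.5.1.3.1 has "every 6 weeks (± 7 days) counting from Cycle 1 Day 1". Under Section 9.4.1.1, a delayed dose resets the cycle days, "but will exclude response assessments as outlined in Section 9.5.1.3", so scan dates stay tied to the first dose.

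The sequence notes also use 97 days in another place. A subject with a baseline scan but no post-baseline scan is censored at first dose, unless death occurs "within 97 days after the first dose date and did not receive any new anticancer therapy", in which case it is an event.

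**The concern.** The day threshold is meant to stand in for a count of missed scans. If it lies inside the range that one missed scan can produce, a subject who missed one scan is handled as if two had been missed. The PFS event is then removed and replaced by censoring at the scan before the gap. The rule will be programmed literally, so the number decides the case. The SAP does not show how 97 was obtained, so a programmer cannot tell from the text that the boundary is off.

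**Working it through.** **Inputs.** Scan interval 42 days and window ± 7 days (SAP Section 5.4.2.4; Protocol Section 9.5.1.3.1 and Table 7, footnote s). Anchor: Cycle 1 Day 1. Days below are days after first dose, so scan k is due at 42k ± 7.

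**Reproducing 97.** The natural combinations are:
- 2×42 = 84
- 2×42 + 7 = 91
- 2×(42 + 7) = 98
- 2×(42 + 7) − 1 = 97

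Only the last gives 97, and the SAP does not state the subtraction of one day. Because the operator is >, a limit of 97 already means 98 days or more. Subtracting 1 puts the 98-day gap on the wrong side.

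**Gap between two in-window scans with m scans missed between them:** 42(m + 1) ± 14.

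| Scans missed | Shortest gap | Longest gap |
|---|---|---|
| 0 | 42 − 14 = 28 | 42 + 14 = 56 |
| 1 | 84 − 14 = 70 | 84 + 14 = 98 |
| 2 | 126 − 14 = 112 | 126 + 14 = 140 |

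Any cut-off from >98 to >111 separates one missed scan from two. A cut-off of >97 does not.

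**Example.** Scan 1 is on day 35 (42 − 7), scan 2 is missed, and scan 3 is on day 133 (126 + 7) and shows progression. The gap is 133 − 35 = 98, which exceeds 97. Row 7 censors the subject at day 35 instead of counting an event at day 133, although one scan was missed.

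**How often the boundary is hit.** Each scan has 15 possible in-window days, so there are 15×15 = 225 date pairs with one scan missed. One pair exceeds 97 days and none exceeds 98.

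**From first dose.** First dose is the anchor and has no window, so the first two scan windows are days 35–49 and 77–91 (84 ± 7). The second closes on day 91. The 97-day limit from first dose therefore runs 97 − 91 = 6 days past that point (days 92–97).

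**The case against.** **The threshold is itself the definition.** The footnote defines more than one missed assessment as a gap above 97 days, and the scan interval is only given as a reason. That is fair as to form. But the sequence notes state the rule as two or more missed assessments, and the reason given produces 98, so the mismatch remains.

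**The result depends on the anchor and on how days are counted.** Protocol Section 9.3.3 times Follow-Up scans from the last assessment. On that reading one missed scan gives at most 84 + 7 = 91 days, and the 98-day case does not arise in that period. This stands as a limit on the point, but it does not explain 97 either. A simple date difference gives 98 and inclusive counting gives 99. Only counting the days strictly between the two scans would give 97, and the SAP defines no such convention.

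**No single gap cut-off reproduces a windowed schedule exactly.** This also stands. After an on-time scan on day 42, a death on day 134 comes after the windows of the next two scans have closed (days 77–91 and 119–133), yet the gap is only 134 − 42 = 92 days. Under >98, deaths 92 to 98 days after that scan still count as events. The claim for >98 is narrower: it never censors a subject for one missed in-window scan.

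**A stronger reading to avoid.** A reader might infer that the 97-day limit from first dose is also an error, because deaths on days 92–97 count as events although row 7 would censor them. The documents do not support this. Row 7 uses a gap above 97 days from the last adequate assessment, not 91 days from first dose, and subjects with no post-baseline scan are handled by their own note, which comes earlier in the stated sequence. The scan-to-scan rule allows similar slack, as the previous paragraph shows. A limit of 91 would be a different convention. What can fairly be asked is where 97 comes from, since the schedule reason is attached only to the scan-to-scan footnote.

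**Conclusion.** The scan-to-scan threshold is one day too low for the schedule it cites. A 98-day gap with one missed scan is censored under a rule meant for two or more. This rests on scans being counted from Cycle 1 Day 1, both scans falling within ± 7 days, and gaps being simple date differences.

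The effect is very small. It needs one scan exactly 7 days early, one missed, and the next exactly 7 days late. PFS is a secondary endpoint summarised descriptively, and SAP Section 5.3.3 plans no statistical comparisons. Dose escalation ended early and there is no expansion part, although PFS is not among the analyses that SAP Section 7 removes. With the planned figure of about 35 subjects, one subject carries 1/35 = 2.9% of the weight. That is not an estimate of how many are affected, and the documents do not show that any subject is.

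The limit from first dose is an unexplained convention and is not shown to be wrong.

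**What to change.** In the double-asterisk footnote to SAP Table 3, change the threshold to >98 days and add the derivation: 2×(42 + 7) = 98, the longest gap that one missed in-window scan can produce. State that gaps are simple date differences.

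For the limit counted from first dose, either state the basis of 97 days or align it with the schedule, where the second scan window closes on day 91.

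The cost is one number and a few words in the SAP, with the matching line in the program. No new data and no design change are needed.
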